**N°ID-RCB: 2020PI095**

**Update 10 / 08 / 2021**

Acronym : PRODDIGE  Full title: Digital solution to improve cognitive function in epilepsy: PRODDIGE project

1.1 Research characteristics

 
- Clinical research
 
- Multicentric
 
- Transversal : patient / normal control
 
- Randomized trial
 

1.2 Product(s)/strategy observed in the research

Randomized controlled trial to evaluate the use of a digital solution on epileptic patients' cognitive complaint about lexical access disorder.

1.3 Research Rationale and Working Hypotheses

Epilepsy is one of the most common chronic neurological conditions. It leads to cognitive disorders in 20-50% of patients. In comparison to seizures, these cognitive disorders are a major additional factor in occupational, social and family disability. They are particularly frequent (50%) in temporal epilepsies and concern most of time memory and language skills. These disorders are well described, multifactorial, but no therapy (drug and/or non-drug) has yet been validated (Brissart & Maillard 2018).
 
Recently, cognitive rehabilitation techniques have shown benefits in some neurological pathologies, such as multiple sclerosis (Brissart et al. 2020).
 
In adult epilepsy, few cognitive remediation studies that have been conducted have significant methodological shortcomings that limit the scope of their results (for review Del Felice et al, 2017; Joplin et al, 2018).
 
Studies have shown promising results in attention and memory (Engelberts et al., 2002; Helmstaedter et al., 2008) but in language, no study has been published.
 
Our objective is to evaluate the effectiveness of a digital solution with language exercises in epileptic patients.

1.4 Main Objective

Evaluate the use of digital solution in total autonomy and compare it to the use of a neuropsychologist-supervised via teleconsultations with a sample of epileptic patients.

1.5 Primary endpoint

Number of weekly connections of epileptic patients in each group.

1.6 Secondary objectives

To compare the cognitive and behavioral abilities of patients before and after the program:
 
 
- Feeling the frequency of lexical access problems
 
- Self-esteem,
 
- Score and speed of oral naming
 

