### **1.8 Number of Subjects required**

Main hypothesis: Investigators postulate that the group of participants supervised by a psychologist via teleconsultations will have an average weekly number of connections at least twice as high as that measured in the total autonomy group.

Secondary hypothesis: Participants who use the solution should have a lower frequency of lexicon access disorders than participants who do not use it. This study should make it possible to assess its extent and discuss its clinical relevance.

To test these hypotheses, 3 groups of participants will be constituted:

- 1 group "application supervised by a psychologist via teleconsultations" (n=30)

- 1 group "application in total autonomy" (n=30)  
- 1 "control" group without using the application (n=30).  
A 4th group of "healthy controls" (n=70) will also be needed to calculate the "reliable change index" (an index that evaluates the potential learning effect when a cognitive test is performed twice over a period of less than one year). The larger size of the latter group is justified by the expected higher number of people lost to follow-up on the second visit.

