### 1.11 Criteria for inclusion of subjects

#### Inclusion criteria of epileptic participants:

Patient with epilepsy, according to Fisher et al. (2005) criteria: all type of epilepsy could be include (new-onset and drug-resistant)

Treatment must have been stable for 4 months: have the same molecule

Person who has received full information about the organization of the research and has not objected to his or her participation and the use of his or her data

Person aged 18 and over

Mandatory affiliation to a social security scheme

Validated cognitive inclusion criterion: having a YES response on the cognitive complaint questionnaire :

A.Spontaneous complaint :

Does the patient spontaneously complain of language difficulties?

B.Subjective complaint :

1. Do you search for your words?

2. Do you sometimes feel like you have the word on the tip of your tongue?

3. Do you sometimes have trouble finding the names of people you know well?

4. Do you ever say one word for another?

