**1.14 Search process**

**I. PATIENT COURSE :**

Inclusion visit as part of the usual follow-up:

- Participants and subjects will be informed of the study by an investigator during a consultation at their respective centers.

- A neuropsychologist will carry out the consultations

- After verification of the eligibility criteria by the investigator and presentation of the objectives of the study, an information document will then be given to the patient for an attentive reading.

- After a reflection period, if the patient agrees to participate in the research and has not objected to the use of these data in this research, then randomization will be carried out via an online module (CleanWeb). This individual randomization will be done according to a 1:1 ratio with stratification by age (+/-5 years) and socio-educational level (+/- 2 years of study) and a randomization block of 4.

- The neuropsychological assessment (V1) will be carried out by the psychologist: it consists of questionnaires and cognitive exercises lasting one and a half hours (the cognitive functions tested are listed in paragraph 1.8).

- The characteristics of each patient's epilepsy will be collected from his or her computerized medical record.

Depending on the group obtained by randomization (A/ B / C), the psychologist will present the application to the patient or not, and will inform him or her whether or not he or she will have telephone appointments.

At the end of visit 1, participants will be invited to use the digital application at their convenience for the autonomous group (B). Participants in the teleconsultation group (A) will be called once a week for 16 weeks to follow up on their connection to the application and to check that they do not present any particular difficulties in using it. A link will be provided to download the application. It will be sent to the patient on paper at the end of the visit.

The duration of use of the digital application will be 4 months.

Group C participants do not use the digital application.

➤ **Follow-up visit (V2) = 5 months post-inclusion (research specific)**

During this visit, participants in group A, B or C will undergo a neuropsychological assessment. The patient in group A or B will provide to the psychologist his or her number of connections to the application.

The patient in group A or B will also answer an interview on how he or she feels about using the application.

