**I. NORMAL CONTROL COURSE :**

➤ **Inclusion visit (research specific)**

Normal controls are recruited through posters and on a voluntary basis in the 4 centers. They are therefore in contact (telephone or e-mail) with the neuropsychologist of the study on their own initiative. The objectives of the study are then presented during this contact. If the subject gives his agreement, an appointment is fixed in order to carry out the inclusion visit. On the day of the visit, the subject is given an information document that he or she should take the time to read. After a period of reflection, if he agrees to participate in this research and if he does not object to the use of his data within the framework of this research, the acts specific to the research may be carried out (neuropsychological assessment including only cognitive data + collection of clinical characteristics).

➤ **Follow up visit : 5 months post inclusion (research specific)**

During this visit, the normal control will undergo the same neuropsychological assessment as in visit V1 with the neuropsychologist.

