## 1.19 Statistical Analysis

Descriptive analysis: The parameters collected will be described in each group by percentages (categorical variables), mean +/- standard deviation, quartiles, and extreme values (continuous variables).

Main analysis: the comparison of the mean number of connections will first be carried out by a parametric (Student's t) mean comparison test or its non-parametric (Man-Withney) equivalent if the hypotheses of normality and equality of variances are not verified. In the case of significant

differences in one or more parameters between the 2 groups compared, these adjustment variables will be introduced into a linear regression model. A stepwise selection method is provided.

Secondary analysis: Before-after comparisons will be performed by tests on paired series, the Student's t-test when the variable to be compared is quantitative (or the Wilcoxon test), and Mac Nemar's Chi2 when the variable to be compared is qualitative.

The value of the "Reliable Change Index" will be obtained in the group of healthy controls by the product of the standard error of the score concerned and the standard deviation of the difference observed at 2 measurement times.

The significance threshold is set at 5%. An a posteriori power calculation is also planned.

The analyses will be performed by the UMDS, using SAS v9.4 software (SAS Institute Inc., Cary, NC, USA).

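### Section 1.19 plans no test or interval comparing the application arms with randomised control arm C, so the users-versus-non-users hypothesis in section 1.8 is left untested

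*Protocol*

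**What the plan says.** Section 1.8 gives the secondary hypothesis as a contrast between people: "Participants who use the solution should have a lower frequency of lexicon access disorders than participants who do not use it". It continues "To test these hypotheses, 3 groups of participants will be constituted", and lists A (supervised application), B (autonomous application) and C (no application), 30 patients each.

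Section 1.6 words the secondary objective differently, as change over time: "To compare the cognitive and behavioral abilities of patients before and after the program".

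Section 1.19 follows 1.6. For secondary outcomes it states "Before-after comparisons will be performed by tests on paired series" and names the paired t-test, Wilcoxon and McNemar. Its two-group test (t or Mann-Whitney) and the regression adjustment attached to it concern the number of connections. Arm C appears only descriptively: "The parameters collected will be described in each group".

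Arm C does supply follow-up data. Section 1.14 says that at V2 "participants in group A, B or C will undergo a neuropsychological assessment". The Reliable Change Index in 1.19 comes from the separate healthy-control group, whose visit is a "neuropsychological assessment including only cognitive data" plus clinical characteristics.

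**The concern.** A before-after test asks whether scores moved within a group. It does not ask whether they moved more with the application than without it. Three other causes of movement are present in this design:

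- **Practice.** Section 1.8 itself expects a learning effect when a cognitive test is repeated within a year.
- **Time**, over the five months between visits.
- **Regression to the mean.** Under 1.11, patients enter by "having a YES response on the cognitive complaint questionnaire", so complaint scores may fall on retest for that reason alone.

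The randomised arm C is what would remove these, yet 1.19 plans no test or interval for the difference from C. Followed literally, the trial could report significant improvement under an application that does nothing, and would give no estimate of its effect. Placing separate paired results side by side (significant in A, not in C) is not a test of the difference either.

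**Working it through.** **1. Which tests reach arm C?**

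| Item in 1.19 | Outcome | Groups | Inference against C? |
|---|---|---|---|
| Descriptive | all | each group | no |
| Main test and regression | connections | two; C has no application, so A vs B | no |
| Secondary tests | secondary scores | within patient, V1 to V2 | no |
| Reliable Change Index | cognitive scores | healthy controls, not randomised | no |

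No row tests the hypothesis in 1.8. This follows from the text alone; the figures below only illustrate the consequence. There is no planned figure to reproduce first, because 1.8 gives 30 per group without a mean, SD, power or secondary effect size.

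**2. Paired test when the application does nothing.** From the protocol: n = 30 per arm and a 5% threshold (two-sided assumed). Assumed: a common shift s of 0.2–0.4 SD from practice or time, and a V1–V2 correlation r of 0.6–0.8. The SD of the difference is √(2(1−r)), the non-centrality is s√n/√(2(1−r)), and power comes from the non-central t.

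| s, r | SD of difference | Non-centrality, n=30 | P(significant), n=30 | P(significant), n=60 |
|---|---|---|---|---|
| 0.2, 0.6 | 0.894 | 1.22 | 0.220 | 0.399 |
| 0.3, 0.7 | 0.775 | 2.12 | 0.536 | 0.839 |
| 0.4, 0.8 | 0.632 | 3.46 | 0.917 | 0.998 |

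The n=60 column applies if A and B are pooled, which 1.19 does not specify. With independent arms, the chance of a significant result in A but not in C is p(1−p). Over the 3×3 grid of s and r it runs from 0.917 × 0.083 = 0.076 to 0.536 × 0.464 = 0.249.

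**3. Regression to the mean alone, language questionnaire, n = 30.** Assume entry selects directly on the V1 score and takes the most-complaining fraction q. This is an upper bound. The shift is (1−r)φ(c)/q, where c is the normal cut-off, and the variance of the difference is (1−r)²·Var(V1 | selected) + 1 − r². For q = 0.5 and r = 0.7: shift 0.3 × 0.798 = 0.239; variance 0.09 × 0.363 + 0.51 = 0.543; SD 0.737; P = 0.406.

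| q | r=0.6 | r=0.7 | r=0.8 |
|---|---|---|---|
| 0.3 | 0.844 | 0.712 | 0.522 |
| 0.5 | 0.525 | 0.406 | 0.282 |
| 0.9 | 0.076 | 0.069 | 0.063 |

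**4. The comparison that is missing.** Regressing V2 on arm (60 vs 30) and V1, with 20,000 simulated trials per setting and the three shifts of step 2, gave rejection rates of 0.0511, 0.0494 and 0.0489. The common shift cancels and the error rate is nominal.

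**5. What that comparison could detect.** At 80% power with a two-sample t-test on change, the detectable difference is 0.633 SD of change for 60 vs 30 and 0.736 for 30 vs 30. With adjustment for V1, multiply by √(1−r²) and read the result in SDs of the score. For r = 0.6, 0.7 and 0.8 this gives 0.507, 0.452 and 0.380 (60 vs 30), and 0.588, 0.525 and 0.441 (30 vs 30).

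**The case against.** The main objective and primary endpoint concern use of the application, A versus B, and are untouched. Section 1.8 adds that the study should allow the extent of the effect to be assessed and its relevance discussed, which reads as partly exploratory. Sections 1.6 and 1.19 agree with each other, and an unseen SAP might add the contrast. The 70 healthy controls are there precisely to address retest learning. Entry by a YES to common word-finding questions is probably lenient, so regression to the mean may be slight. Pooling A and B is not the protocol's idea, and its main hypothesis expects their use to differ at least twofold.

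Part of this stands:

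- The 52%–84% range in step 3 is no expected error rate. If 90% of patients would pass entry, the figure is 6%–8%. The protocol also does not say that the entry questionnaire is the 0–12 language score.
- The shifts and correlations in step 2 are assumptions.
- Dropout would reduce precision. With an assumed 15%–20% loss, the unadjusted detectable differences become about 0.69–0.71 SD (A+B vs C) and 0.80–0.83 SD (one arm vs C).

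The core is not answered. Section 1.19 does fix the secondary analysis, and fixes it as a method that cannot test what 1.8 says will be tested; an SAP that added the contrast would depart from 1.19. The Reliable Change Index rests on non-randomised volunteers, does not cover the self-reported questionnaire and involves no comparison with C. Estimating the extent of an effect also needs a between-arm difference. A+B versus C is the pooling that the users-versus-non-users wording implies.

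**Conclusion.** The concern holds, and it should be corrected before analysis. The secondary hypothesis in 1.8, the only efficacy hypothesis the protocol states, has no inferential test in 1.19, although arm C is randomised and reassessed at V2. That conclusion rests on the text and needs no assumption.

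The size of the risk does rest on assumptions. With a common shift of 0.2–0.4 SD and a correlation of 0.6–0.8, a useless application gives a significant paired result in 22% to 92% of trials in a given arm, or 40% to over 99% if A and B are pooled. A result significant in A but not in C occurs in 8% to 25%. Regression to the mean adds anything from almost nothing to a large share, depending on how selective entry is.

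**What to change.** Reword 1.6, 1.8 and 1.19 so that objective, hypothesis and test ask the same between-group question:

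- For each secondary score, fit a linear model of V2 on randomised arm, adjusted for V1, age and years of education (continuous), with patients analysed in the arm assigned.
- Name one principal contrast for the secondary hypothesis: A+B versus C on the language questionnaire (0–12), tested at 5%. This outcome matches the item in 1.6 on the felt frequency of lexical access problems.
- Report A versus C, B versus C and all other scores as supporting estimates with 95% confidence intervals and no claim of significance.
- Report missing V2 by arm, and repeat the principal contrast in a mixed model of V1 and V2 (common V1 mean, arm-by-visit term), which keeps patients without V2.
- Keep the paired changes as description.

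The essential change is the planned V1-adjusted comparison with C. The covariate form and the mixed model can be settled in the SAP.

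The cost is text only: V1, V2, age, years of study and arm are already collected. The limited precision shown in step 5 should be stated openly, since a non-significant contrast would not show that the application has no effect.

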### **1.7 Secondary Evaluation Criteria**

Scores at :

- Questionnaire language score (0 to 12 points)
- Depression scale score (Neurological Disorder Depression Inventory for Epilepsy : NDDI-E) : 6 to 24 points : 6 better outcome
- Anxiety scale score (Generalized Anxiety Disorder: GAD-7): 0 to 21 points : 0 better outcome
- Self-esteem score (Rosenberg scale): 0 to 40 points: 40 better outcome
- Number of correctly named words and response time (Batterie d'Evaluation des Troubles Lexicaux) : 0 to 50 points : 54 = better outcome
- Computerized Speed Cognitive Test (CSCT): processing speed index: number of correct items in 90 sec. 0 to 110 points : 110 = better outcome
- Immediate memory: digit span: number of digits recalled correctly in location order: 0 to 9 score : 9 = better outcome
- Working memory: backward digit span: number of digits recalled correctly in inverse order: 0 to 9 score : 9 better outcome
- Selective Attention Test: Paced Auditory Serial Audition Test 4 seconds (PASAT): 0 to 60 score : 60 = better outcome
- Verbal Initiation Test: Phonological Fluency: number of words beginning with P given in 2 minutes: 0 to 50 words : 50 = better outcome
- Category fluency test: number of words given in 2 minutes that belong to the category of Animals: 0 to 50 words : 50 = better outcome
- Boston Naming Test (BNT): number of correctly named words (0 to 50 points) and response time in seconds : 50 = better outcome
- Lexicon access tests (Denomination Orale 80): number of correctly named words (0 to 80 words) and response time in seconds : 80 = better outcome

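### The Reliable Change Index is written as a product of two score-unit terms with no mean retest gain, so it cannot be compared with a patient's change

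*Protocol*

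**What the plan says.** Protocol section 1.19 (Statistical Analysis) gives one formula for the RCI. Its value comes from the healthy controls, "by the product of the standard error of the score concerned and the standard deviation of the difference observed at 2 measurement times".

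Section 1.8 (Number of Subjects required) describes the RCI as "an index that evaluates the potential learning effect when a cognitive test is performed twice over a period of less than one year" and gives it as the reason for a fourth group of 70 healthy controls. Under the normal control course in section 1.14, at 5 months "the normal control will undergo the same neuropsychological assessment as in visit V1 with the neuropsychologist".

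The scores in section 1.7 are on very different scales. Digit span is the "number of digits recalled correctly in location order: 0 to 9 score : 9 = better outcome"; the CSCT is the "number of correct items in 90 sec. 0 to 110 points : 110 = better outcome". The naming test DO 80 yields a "number of correctly named words (0 to 80 words) and response time in seconds".

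The Protocol gives no other RCI formula. It also gives no score SD, retest reliability or expected retest gain.

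**The concern.** There are two faults in the formula as written.

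1. **Units.** A standard error of a score and an SD of a difference are both in score units. Their product is in score units squared, whether the standard error is that of measurement or that of the mean. A change score is in score units, so the two cannot be compared.
2. **No retest gain.** Both terms measure spread. Neither measures how much people improve on average by taking the test a second time, which is what section 1.8 says the index is for.

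The 70 controls are the largest group in the study (each patient arm has 30), and they attend two research-specific visits to supply this index. Applied as written, the index would not separate practice from real change, and one nominal rule would be lax on short-range tests and strict on long-range ones.

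**Working it through.** The Protocol has no numerical RCI to reproduce. The SD, reliability (r) and gain values below are therefore assumptions, shown over ranges.

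**Definitions**
- Standard error of measurement: SEM = SD × √(1 − r)
- SD of the V2 − V1 difference: SDdiff = SD × √(2(1 − r))
- Standard error of the mean: SD/√n, with n = 70 (section 1.8)

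**Step 1: units.** Take a response time with SD 0.5 s and r = 0.80.
- In seconds: SEM = 0.2236, SDdiff = 0.3162, product = 0.071 s².
- In milliseconds: 223.6 × 316.2 = 70,711 ms².

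The same change of 0.5 s (500 ms) exceeds the first figure and falls far below the second. The ratio change/SDdiff is 1.58 in either unit. The conclusion drawn from the product depends on the unit of recording.

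**Step 2: behaviour if used as a cut-off.** Assume no true change, no practice gain and normally distributed differences. The two-sided proportion flagged is

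2Φ(−cut-off/SDdiff) = 2Φ(−SEM × SDdiff/SDdiff) = 2Φ(−SEM).

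If the standard error is that of the mean, it is 2Φ(−SD/√70), which needs no r.

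| Score SD | SEM reading, r = 0.80 (r from 0.7 to 0.9) | Standard error of the mean, n = 70 | Valid 95% rule |
|---|---|---|---|
| 1 | 65% (58% to 75%) | 90% | 5% |
| 2 | 37% (27% to 53%) | 81% | 5% |
| 5 | 2.5% (0.6% to 11%) | 55% | 5% |
| 10 | about 0% (at most 0.2%) | 23% | 5% |

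For example, at SD 2 and r = 0.80, SEM = 0.894 and 2Φ(−0.894) = 0.371. The two readings differ in level, but both vary with the scale of the score.

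**Step 3: the missing gain on its own.** Suppose the units were right and the cut-off were 1.96 × SDdiff, but the mean gain were not subtracted. With a gain of g × SD and r = 0.80, SDdiff = SD × √0.4, and the proportion of people showing only the average practice gain who are flagged as improved is 1 − Φ(1.96 − g/√0.4):
- g = 0.2: 5.0%
- g = 0.3: 6.9%
- g = 0.5: 12.1%

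The intended figure is 2.5%.

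**Step 4: a corrected index for comparison.** With SD 5, r = 0.80 and a control mean gain of 2 points, SDdiff = 3.162. The range expected without real change is 2 ± 1.96 × 3.162, or −4.20 to +8.20 points. The Protocol's product for the same inputs is 2.236 × 3.162 = 7.07 points squared (SEM) or 0.598 × 3.162 = 1.89 points squared (standard error of the mean), with no centring on the gain.

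**The case against.** - **The wording may be a translation slip** for a normal quantile times SDdiff. That would remove the unit fault, but the text does not say it, and the mean gain would still be missing.
- **The gain could be subtracted elsewhere.** Section 1.19 plans means and SDs for each group, so the controls' gain will be obtainable, and an RCI without a practice term is a recognised form. This makes the second fault the lesser one. It remains a fault against the purpose stated in section 1.8.
- **A statistical analysis plan may settle it.** How the index is applied to a patient can fairly be left to that document, and its absence here is not held against the Protocol. But the Protocol does state a formula, and a correct analysis plan would contradict it.
- **No section uses the RCI as a cut-off.** The listed secondary tests are paired comparisons. This stands: the flag rates are conditional illustrations, not an estimate of harm. The unit fault does not depend on them.
- **The figure of 70 assumes no loss**, while section 1.8 expects some. With an assumed 50 completers, the rates in the standard-error-of-the-mean column become about 89%, 78%, 48% and 16%. The dependence on scale is unchanged.

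**Conclusion.** The concern holds: the formula is wrong as written. The unit fault follows from the definition alone and needs no assumption. The missing gain follows from setting section 1.19 beside section 1.8. The size of the effect depends on the assumed SD, reliability and gain, and on the product being used as a cut-off for individual change. On those terms, false flagging at r = 0.80 runs from 65% to about 0% as the SD goes from 1 to 10.

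The fault is confined to the interpretation of the secondary cognitive scores. The number of weekly connections, its main analysis and the paired secondary tests are untouched. It should be fixed, because the index is the stated reason for the healthy-control group.

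**What to change.** Replace the RCI sentence in section 1.19 with a practice-corrected definition, for example:

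RCI = [(V2 − V1) − M] / SDdiff

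Here V2 − V1 is the patient's change, and M and SDdiff are the mean and SD of the V2 − V1 change in healthy controls with both visits, computed separately for each cognitive score. Fix the critical value in advance; 1.96 would match the 5% threshold. Another accepted practice-corrected variant would also do, provided its formula is written out.

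Restrict the definition to the cognitive scores. Sections 1.14 and 1.16 plan cognitive tests only for the controls, so the language questionnaire, NDDI-E, GAD-7 and Rosenberg scores will have no control retest data.

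The cost is one sentence. Both control visits are already planned, so no new data are needed.

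### The a posteriori power calculation in 1.19 has no stated effect; at the observed effect it restates the p-value, and a ratio with its interval would answer the main hypothesis directly

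*Protocol*

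**What the plan says.** The primary endpoint in protocol section 1.5 is "Number of weekly connections of epileptic patients in each group". The main hypothesis in 1.8 is that the supervised group (A) "will have an average weekly number of connections at least twice as high as that measured in the total autonomy group" (B). Section 1.8 fixes 30 patients in each randomised group. It gives no expected mean, SD, target power or dropout rate for those groups.

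For the main analysis, 1.19 says that "the comparison of the mean number of connections will first be carried out by a parametric (Student's t) mean comparison test", with Mann-Whitney as the alternative if normality or equal variances fail. A linear regression follows if the two groups differ on other parameters. The threshold is 5%, with no statement of one or two sides. The section then adds: "An a posteriori power calculation is also planned". This is the only mention of power in the document. It names neither the effect to be used nor the purpose of the result. No ratio, and no confidence interval for A against B, is mentioned.

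**The concern.** Two things in the text do not serve the question the trial asks.

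- **The power sentence is open.** Its usual reading is power at the observed effect, which is the p-value on another scale. As the protocol gives no power before the data, a reader may turn to this figure to judge whether 30 per group was enough, and on that reading it cannot tell them.
- **The test and the hypothesis differ.** The hypothesis is a ratio of at least 2. The planned test addresses a ratio of 1. The regression step estimates a difference, and Mann-Whitney does not estimate a ratio of means.

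At stake is interpretation. After a non-significant result, the trial needs to separate data that rule out a doubling from data that are merely imprecise. After a significant one, it needs to say whether a doubling is supported or only some increase.

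**Working it through.** **Inputs.** n = 30 in A and 30 in B, and a hypothesised ratio of 2 (1.8). Student's t and a 5% threshold (1.19). Two-sided testing is assumed. The coefficient of variation (CV, SD divided by mean) is assumed to lie between 0.5 and 2 and to be the same in both groups, because the protocol gives no SD.

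**The plan's own figure.** The 30 per group cannot be reproduced. A ratio without a mean and SD gives no standardised effect, so 30 can be called neither right nor wrong. For range only, take mean B = 1 and mean A = 2, so that the standard error (SE) of the difference is CV × √(5/30). Power = Φ(1/SE − 1.96), which is 0.998, 0.90, 0.69, 0.37 and 0.23 at CV 0.5, 0.75, 1, 1.5 and 2.

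**Power at the observed effect.** With 58 degrees of freedom the critical value is 2.002. Observed power is P(|T| > 2.002), where T is noncentral t with noncentrality equal to the observed t. The observed t is itself determined by p, so no other feature of the data enters.

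| p | observed t | observed power |
|---|---|---|
| 0.01 | 2.663 | 0.745 |
| 0.05 | 2.002 | 0.503 |
| 0.20 | 1.296 | 0.247 |
| 0.50 | 0.679 | 0.102 |

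Every non-significant t-test therefore shows about 50% or less.

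**One p-value, different situations.** Work on the log-ratio scale with SE = CV × √(2/30) = 0.258 × CV. Fix p = 0.20, so that log(ratio) = 1.282 × SE. The 95% interval is exp(log ratio ± 1.96 × SE). Power for a ratio of 2 is Φ(0.693/SE − 1.96).

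| CV (assumed) | observed ratio | 95% interval | observed power | power at ratio 2 |
|---|---|---|---|---|
| 0.5 | 1.18 | 0.92 to 1.52 | 0.25 | 1.00 |
| 1.0 | 1.39 | 0.84 to 2.31 | 0.25 | 0.77 |
| 1.5 | 1.64 | 0.77 to 3.51 | 0.25 | 0.43 |
| 2.0 | 1.94 | 0.70 to 5.33 | 0.25 | 0.27 |

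In the first row the data exclude a doubling. In the last they are uninformative. Observed power is the same in both. Power at a ratio of 2 separates the rows, and the interval separates them and also gives the estimate.

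**Equality against doubling.** If the observed ratio is exactly 2, the interval is 2 × exp(±1.96 × SE):

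- CV 0.5: 1.55 to 2.58
- CV 0.75: 1.37 to 2.92
- CV 1.0: 1.21 to 3.32
- CV 1.5: 0.94 to 4.27
- CV 2.0: 0.73 to 5.50

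At CV 1.0 equality is excluded, yet ratios well below 2 remain compatible. For the lower limit to reach 2 at that CV, the observed ratio would have to be 2 × 1.66 = 3.32. Rejecting equality and supporting a doubling are different findings.

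**The case against.** The strongest reply is that the protocol never says the observed effect will be used. It has a target effect and no SD, so a natural reading is power at a ratio of 2 with the SD found in the data. That would not restate the p-value and would say something about 30 per group, as the last column of the second table shows. This stands. A reader might infer that the planned calculation is bound to be empty, but the text supports only that its effect is unspecified and that its usual meaning is uninformative.

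Three further points stand in part.

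- The exact link to p belongs to the t-test. Under Mann-Whitney, a plausible route for connection counts, it is approximate.
- A reader might infer that a null result will be explained away, or a significant one presented as proof of doubling. No passage ties the power figure to a decision or a rule of interpretation, so this is conjecture.
- The choice of interval method is ordinary material for a statistical analysis plan, which is not shown here. The group means and SDs promised in 1.19 would also let a reader work out a rough ratio and interval. The doubling could be read as an expected effect, since 1.4 speaks only of comparing the two modes of use.

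What survives does not rest on missing detail. The power sentence is a stated commitment, and 1.8 words the main hypothesis as at least a doubling while 1.19 tests equality.

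**Conclusion.** The point holds in limited form. Section 1.19 commits to a power calculation after the data without naming its effect. In the usual meaning, with a t-test at 30 versus 30, the answer is about 50% at p=0.05, 25% at p=0.20 and 10% at p=0.50, and it adds nothing to the p-value. At the pre-stated ratio of 2 with the observed SD it would be informative, though less direct than an interval. The planned test of equality does not address the hypothesis of at least a doubling.

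The observed-power figures assume two-sided testing and 30 analysed per group. The interval widths rest wholly on assumed CVs and illustrate precision only. They do not show that 30 per group is too few, and a reader should not infer that. Nor does an interval supply the justification of 30 that 1.8 lacks, which needs an assumed mean and SD before the data. The primary test and its threshold are unaffected; what improves is what the result can be said to mean.

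**What to change.** In 1.19, replace the a posteriori power sentence with one to this effect: the ratio of mean weekly connections, supervised over autonomous, will be reported with a 95% confidence interval (for example by bootstrap or a log-link model) and interpreted against both 1 and the hypothesised 2. An interval wholly below 2 excludes the doubling, one containing 2 allows it, and one wholly above 2 supports it.

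If a power figure is kept, state that it is computed at the hypothesised ratio of 2 with the observed SD, and not at the observed effect.

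The cost is one sentence. The connection counts are already collected at the second visit, and no visit, measurement or patient is added. Justifying 30 per group in 1.8 is a separate task that this change does not discharge.
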